A subject will be regarded as having completed Part A if they complete all phases of Part A (Pre-Screening/Screening/Run-in, Treatment, and Follow-up). Subjects who complete Part A will participate for approximately 22 weeks.

Long-Term Safety / Pharmacodynamic Phase (Part B)

At the end of Part A, a benefit/risk assessment will be performed by the Investigator and if this assessment supports continued therapy with mepolizumab the subject can continue into Part B following the Part A Follow-up (Visit 8).

Long-Term Treatment: Those subjects meeting the eligibility criteria for the long-term phase of the study at Visit 9 will receive mepolizumab 40 or 100 mg SC, (depending on subject bodyweight measured at Visit 9; 40 mg for subjects <40 kg and 100 mg for

subjects ≥ 40 kg). Subjects should be monitored post-SC administration according to standard practice at the site.

[figure not shown]
From Visit 10 onwards subjects will receive mepolizumab at 4-weekly intervals for a total of 48 weeks. Subjects with bodyweight <40 kg at Visit 9 should be weighed at each subsequent visit and have their dose adjusted once their bodyweight exceeds ≥ 40 kg.

Follow-up: Following completion of Visit 22, subjects not transitioning to the long term access program will enter into the Follow-up phase which will consist of one additional follow-up visit at week 80 (Visit 23).

Study visits in Part B will have a window of ± 5 days. The total duration of Part B is approximately 60 weeks (52 weeks for subjects transitioning to the long-term access program). A subject not transitioning to the long term access program will be regarded as having completed Part B if they complete all phases of Part B (Long-Term Treatment and Follow-up). A subject transitioning to the long term access program will be regarded as having completed Part B if they complete all the Treatment phase of Part B.

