6.8. Treatment after the Completion of Part A and Part B

The investigator is responsible for ensuring that consideration has been given to the post-study care of the patient's medical condition whether or not GSK is providing specific continuing study treatment under Part B of this study.

At the end of Part A, a benefit/risk assessment will be performed by the Investigator and if this assessment supports continued therapy with mepolizumab the subject will be offered the opportunity to enrol in Part B following the Part A Follow-up visit (Visit 8). Part B will continue for 52 weeks of additional mepolizumab treatment.

At the end of Part B, when feasible, subjects will transition to a long term access program. At the end of the Treatment Phase of Part B, subjects that are not able to transition to the long term access program will return to usual care and will be prescribed appropriate alternative asthma therapy, as required.

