Bodyweight	X	X ¹	X ¹	X ¹	X ¹	X ¹	X ¹	X ¹	X ¹	X ¹	X ¹	X ¹	X ¹				
Adverse events	X	X	X	X	X	X	X	X	X	X	X	X	X	X	X	X	
Cardiovascular events	X	X	X	X	X	X	X	X	X	X	X	X	X	X	X	X	
Liver events	X	X	X	X	X	X	X	X	X	X	X	X	X	X	X	X	
Laboratory Assessments²																	
Urinalysis	X ¹					X								X		X	
Pregnancy Test	U	U	U	U	U	U	U	U	U	U	U	U	U	U	U	U	
Blood sample for immunogenicity ²							X						X		X	X	
Outcomes Assessments																	
FEV1	X ¹			X			X			X			X	X	X	X	
ACQ-7	X ¹			X			X			X			X	X	X	X	
C-ACT	X ¹			X			X			X			X	X	X	X	

Procedure	Eligibility Check / First Dose	Treatment Period												Exit Visit	Follow-up ³	Early Withdrawal
Visit	9	10	11	12	13	14	15	16	17	18	19	20	21	22	23	
Week of Study (visit window \pm 5 days)	20	24	28	32	36	40	44	48	52	56	60	64	68	72	80	
Assessment of exacerbation	X	X	X	X	X	X	X	X	X	X	X	X	X	X	X	X
Investigational Product																
Mepolizumab SC dose administered	X	X	X	X	X	X	X	X	X	X	X	X	X			
Study Administration																
Email to GSK Operational Lead	X	X	X	X	X	X	X	X	X	X	X	X	X	X	X	X
Complete eCRF	X	X	X	X	X	X	X	X	X	X	X	X	X	X	X	X

1. Bodyweight will be measured at Visit 9 and at each visit until such time as the subject reaches 40kg in weight. Subjects with bodyweight \geq 40Kg at Visit 9 will not be weighed again during Part B.
2. All laboratory samples should be collected prior to the administration of study medication
3. The 12-week post-dose follow-up visit (Visit 23) is not required for subjects transitioning to the long-term access program.

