4. ANALYSIS POPULATIONS

Table 2 Analysis Populations

Population	Definition / Criteria	Analyses Evaluated
Part A		
All Subjects Enrolled (ASE)	
 All subjects for whom a record exists on the study database. 	
 Pre-screen failures Screen failures Run-in failures
Safety	
 All subjects receiving at least one dose of mepolizumab beginning at Visit 2. 	
 Study Population Safety Immunogenicity
Pharmacokinetic (PK)	
 All subjects receiving at least one dose of mepolizumab beginning at Visit 2 and having at least one blood sample taken at Visit 3 or thereafter with measurable mepolizumab plasma concentration. 	
 Pharmacokinetic
Pharmacodynamic (Blood Eosinophils) (PDe)	
 All subjects receiving at least one dose of mepolizumab beginning at Visit 2 and having at least one Part A blood sample evaluable for blood eosinophil count. 	
 Blood eosinophil count
Pharmacodynamic (Outcome Assessments) (PDo)	
 All subjects receiving at least one dose of mepolizumab beginning at Visit 2 and having at least one Part A assessment of pharmacodynamic outcomes (ACQ-7, C-ACT, asthma exacerbation, FEV₁, IgE or IL-5). 	
 ACQ-7 C-ACT Asthma exacerbations FEV₁ Immunoglobulin E (IgE) IL-5
Pharmacokinetic / Pharmacodynamic (PKPD)	
 All subjects receiving at least one dose of mepolizumab beginning at Visit 2 and having at least one blood sample taken at Visit 3 or thereafter with measurable mepolizumab plasma concentration and who also have 	
 PKPD

Population	Definition / Criteria	Analyses Evaluated
	a baseline PDe measurement and at least one post-treatment PDe measurement.	
Part B		
Safety	
 All subjects receiving at least one dose of study medication beginning at Visit 9. 	
 Study Population Safety Immunogenicity
Pharmacodynamic (Blood Eosinophils) (PDe)	
 All subjects receiving at least one dose of mepolizumab beginning at Visit 9 and having at least one Part B blood sample taken for blood eosinophil count. 	
 Blood eosinophil count

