10.4. Appendix 4: Treatment Phases

10.4.1. Treatment Phases (Adverse Events)

Adverse events will be classified according to time of occurrence relative to the first and last dose of mepolizumab within specific study parts.

Treatment Phase	Definition
Pre-Treatment	AE Onset Date & time < First Part A dose of mepolizumab If mepolizumab treatment is never started then all AEs will be classified as pre-treatment.
On-Treatment (Part A)	First Part A dose of mepolizumab ≤ AE Onset Date & time ≤ Last Part A dose of mepolizumab + 28 days If an AE start date is missing or partial then the AE will be considered on-treatment unless there is evidence to the contrary (e.g. month/year of onset date is present and is earlier than the month/year of First Part A dose of mepolizumab).
Post-treatment (Part A)	For subjects entering Part B: Last Part A dose of mepolizumab + 28 days < AE Onset Date & time < First dose of Part B mepolizumab For subjects not entering Part B: Last Part A dose of mepolizumab + 28 days < AE Onset Date & time ≤ Visit 8 (Week 20) visit date
On-Treatment (Part B)	First dose of Part B mepolizumab ≤ AE Onset Date & time ≤ Last Part B dose of mepolizumab + 28 days If an AE start date is missing or partial then the AE will be considered on-treatment unless there is evidence to the contrary (e.g. month/year of onset date is present and is earlier than the month/year of First Part B dose of mepolizumab).
Post-treatment (Part B)	AE Onset Date & time > Last Part B dose of mepolizumab + 28 days
Onset Time Since 1 st Dose (Days)*	If Treatment Start Date > AE Onset Date = AE Onset Date - First Part A dose of mepolizumab If Treatment Start Date ≤ AE Onset Date = AE Onset Date - First Part A dose of mepolizumab + 1 If Treatment Start Date or AE Onset Date is missing = missing.
Duration (Days)	AE Resolution Date – AE Onset Date + 1
Drug-related	If relationship is marked 'YES' on Inform/eCRF OR value is missing.
* Note: will be derived as time since 1 st dose of mepolizumab utilising the First Part A dose of mepolizumab for both study parts A and B	

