
 • Reporting for tables and figures : 
 • Nominal visits (planned time relative to dosing) will be used in summary figures and summary tables. Actual time relative to dosing will be used in individual subject figures. • The impact of any major deviation from the planned assessment times and/or scheduled visit days on the analyses and interpretation of the results will be assessed as appropriate. • Reporting for Data Listings: 
 • Planned and actual time relative to study drug dosing will be shown in listings (Refer to IDSL Statistical Principle 5.05.1). • Unscheduled or unplanned readings will be presented within the subject data listings • Scheduled visits outside the protocol defined time-windows (i.e. recorded as protocol deviations) will be included in listings, summaries and statistical analyses. The impact of any major deviation from the planned assessment times and/or scheduled visit days on the summaries, figures, analyses will be assessed as appropriate.
Unscheduled Visits

 • When possible unscheduled assessments will be slotted to the closest adjacent scheduled visit. If an unscheduled visit occurs between two completed scheduled visits, the data from the unscheduled visit will not be used in summary tables which are based on by-visit assessments. The information from the unscheduled visit will be included in 'any time post-baseline' summaries and will also be presented in any relevant listings. See Section 10.3 for further details.

Reporting Standards	
Descriptive Summary Statistics	
Continuous Data	Refer to IDSL Statistical Principle 6.06.1
Categorical Data	N (number of subjects in the treatment group), n (number of subjects with non-missing values), frequency, %
Reporting of Pharmacokinetic Concentration Data	
Descriptive Summary Statistics	Refer to IDSL Statistical Principle 6.06.1 Refer to GUI_51487 for further details of handling NQ/BQL values
Reporting of Pharmacokinetic Parameters	

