10.10.3.4. Safety Tables

Safety Tables					
No.	Population	IDSL / TST ID / Example Shell	Title	Programming Notes	Deliverable [Priority]
Exposure					
3.54.	Safety		Summary of Number of Treatments Administered and Time On-Treatment (Part B)	See format of Study Population Table 1.28 (200862 'final' reporting effort)	SAC
AEs					
3.55.	Safety		Overview of All Adverse Events (Part B)	See format of Safety Table 3.01 (200862 'final' reporting effort)	SAC
3.56.	Safety	AE1	Summary of All On-Treatment Adverse Events by System Organ Class (Part B)		SAC
3.57.	Safety	AE5	Summary of All On-Treatment Adverse Events by System Organ Class and Maximum Intensity (Part B)	Add a Total column across all severities	SAC
3.58.	Safety	AE1	Summary of All Post-Treatment Adverse Events by System Organ Class (Part B)		SAC
3.59.	Safety	AE5	Summary of All Post-Treatment Adverse Events by System Organ Class and Maximum Intensity (Part B)	Add a Total column across all severities	SAC
3.60.	Safety	AE3	Summary of On-Treatment Adverse Events by Overall Frequency (Part B)		SAC
3.61.	Safety	AE1	Summary of All On-Treatment Drug-Related Adverse Events by System Organ Class (Part B)		SAC
3.62.	Safety	AE5	Summary of All On-Treatment Drug-Related Adverse Events by System Organ Class and Maximum Intensity (Part B)	Add a Total column across all severities	SAC
3.63.	Safety	AE1	Summary of On-Treatment Adverse Events by Highest Anti Drug Antibody Result At Any Time Post Baseline (Part B)	Add in row with n in each ADA result category	SAC

Safety Tables					
No.	Population	IDSL / TST ID / Example Shell	Title	Programming Notes	Deliverable [Priority]
3.64.	Safety	AE1	Summary of Post-Treatment Adverse Events by Highest Anti Drug Antibody Result At Any Time Post Baseline (Part B)	Add in row with n in each ADA result category	SAC
3.65.	Safety	AE15	Summary of Number of Subjects and Occurrences of Common On-Treatment Non-Serious Adverse Events by System Organ Class (Part B)	≥3% (prior to rounding to nearest percent) XML file to be produced using standard HARP macro	SAC
Serious and Other Significant AEs					
3.66.	Safety	AE1	Summary of Fatal Serious Adverse Events by System Organ Class (Part B)		SAC
3.67.	Safety	AE1	Summary of Non-Fatal Serious On-Treatment Adverse Events by System Organ Class (Part B)		SAC
3.68.	Safety	AE1	Summary of Non-Fatal Serious Post-Treatment Adverse Events by System Organ Class (Part B)		SAC

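### The SAP predates Amendment 5, so the Part B post-treatment adverse event tables keep in their denominator children whose follow-up ends at Week 72

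*SAP*

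**What the plan says.** **SAP.** Section 10.10.3.4 titles Table 3.58 "Summary of All Post-Treatment Adverse Events by System Organ Class (Part B". Tables 3.59, 3.64, 3.68 and 3.70 cover the same phase by intensity, by antibody result, for non-fatal serious events and for all serious events. The Population column reads Safety for all five, and no programming note restricts any of them to children still under observation. Section 4 defines that population for Part B as "All subjects receiving at least one dose of study medication beginning at Visit 9". Section 10.4.1 starts the Part B post-treatment phase at "AE Onset Date & time > Last Part B dose of mepolizumab + 28 days", with no upper limit. Section 10.5.3 gives the contents of categorical displays as "N (number of subjects in the treatment group), n (number of subjects with non-missing values), frequency" and a percentage, without saying which count is the divisor. Section 10.5.1.2 presents Part B in 40 mg, 100 mg, 40/100 mg and overall columns.

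The SAP Synopsis names Amendment 4 as its basis, and Section 2.3 still gives every Part B child a follow-up visit 12 weeks after the last dose.

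**Current protocol (Amendment 5).** Section 7, Table 4, footnote 3: "The 12-week post-dose follow-up visit (Visit 23) is not required for subjects transitioning to the long-term access program". Section 4: "The total duration of Part B is approximately 60 weeks (52 weeks for subjects transitioning to the long-term access program". Section 6.8: "At the end of Part B, when feasible, subjects will transition to a long term access program". Neither document gives the proportion expected to transition, overall or by dose group.

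**The concern.** A child who transitions leaves the study at about the moment the SAP's post-treatment phase opens. The child stays in the Safety N with almost no opportunity to contribute a post-treatment event, and so is counted as event-free. The SAP has no transition flag, no followed-up subset and no summary of post-treatment observation time; Table 3.54 covers time on treatment only.

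These tables are the planned by-dose adverse event summary of the period after about a year of treatment ends. Protocol Section 4.6.1 lists rebound eosinophilia with clinical consequences as a potential risk. In a study of this size, a percentage taken over children who were not watched can give false reassurance.

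A related gap is in SAP Section 10.3.1, which attributes spontaneous events to Part B up to the Visit 23 date. Children who transition will not have that date.

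**Working it through.** **1. The protocol's durations.** From Protocol Table 4, Part B starts at Week 20 (Visit 9), the Exit Visit is Week 72 (Visit 22) and follow-up is Week 80 (Visit 23).
- Full follow-up: 80 − 20 = 60 weeks.
- Transitioning: 72 − 20 = 52 weeks.

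Both match Protocol Section 4.

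**2. Post-treatment observation under the SAP rule.** The last dose in Table 4 is at Visit 21, Week 68. This agrees with Section 4, "From Visit 10 onwards subjects will receive mepolizumab at 4-weekly intervals for a total of 48 weeks": 12 doses from Week 24 to Week 68, 12 × 4 = 48. The on-treatment phase therefore ends at 68 + 4 = Week 72.
- Not transitioning: 80 − 72 = 8 weeks = 56 days.
- Transitioning: 72 − 72 = 0 days.
- With the ±5-day visit window: 5 days if Visit 22 is late, and 5 + 5 = 10 days if Visit 21 was also early.

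**3. Effect on a percentage over the Safety N.** Let p be the incidence among children followed post-treatment and f the share of a column that transitions. Ignoring the few window days, events = p × N × (1 − f), so the displayed percentage is p × (1 − f). With p = 20% (assumed):

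| f (assumed) | Displayed | Factor to recover p, 1/(1 − f) |
|---|---|---|
| 25% | 15% | 1.33 |
| 50% | 10% | 2 |
| 75% | 5% | 4 |
| 90% | 2% | 10 |

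**4. Dose columns.** With p = 20% in both columns and f = 50% in both, each shows 10% and there is no artefact. With f = 50% in one and 90% in the other, they show 10% and 2%. An artefact needs f to differ by column.

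**5. Small-sample reading.** Take N = 28 as an illustrative ceiling (the Part A treatment target; Part B has no set sample size) and f = 50%, leaving 14 followed.
- Three children with an event: 3/28 = 10.7% as planned, 3/14 = 21.4% among those followed.
- No events, upper two-sided 95% limit 1 − 0.025^(1/n): 12.3% for n = 28 and 23.2% for n = 14. With f = 75%, n = 7 and the limit is 41.0%.

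**6. Part B tables not limited by phase** (for example 3.55, 3.66, 3.71, 3.72, 3.74 and 3.93). Here a child who transitions lacks 8 of 60 weeks, 13% of the window. This is a much smaller effect than in the post-treatment tables.

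**The case against.** The strongest reply is that Part B's primary objective is 52-week safety. That is Weeks 20 to 72, common to all completers and summarised in on-treatment tables that this issue does not touch. Part A also has its own post-treatment tables (3.5, 3.6, 3.11, 3.15 and 3.17), with every child scheduled for 12 weeks after the last dose, though after three doses rather than a year. All displays are descriptive. This limits the importance of the point but does not correct the five tables.

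Second, the divisor is inferred. The mock shells sit in supplementary material that is not shown, and other display formats are borrowed from another study. That stands as a condition on the conclusion. The row of n in Table 3.64 does not resolve it, because it counts antibody categories and not children followed.

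Third, Protocol Section 6.8 returns only children who cannot transition to usual care, which implies that those who transition stay on drug. A reader might infer that the tables understate a true off-drug incidence for the whole cohort. The documents do not support that: children who transition have no off-drug experience within the study, and those followed are a selected group. What is diluted is the incidence among children actually followed.

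Fourth, a reader might infer that the dose columns will be unequal. The protocol says only that transition depends on feasibility, so inequality is a risk and not a finding. With 28 children over three columns, about nine each, one child is about 11 percentage points, so a contrast such as 10% against 2% is less than one child.

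Finally, the SAP already separates on- from post-treatment for all events (3.56 and 3.58), non-fatal serious events (3.67 and 3.68) and all serious events (3.69 and 3.70). Under Protocol Section 7.2.1.3, related serious events that the investigator learns of after discharge must still be reported. The tables without a phase limit therefore need little more than a footnote.

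**Conclusion.** The point holds for Tables 3.58, 3.59, 3.64, 3.68 and 3.70. The difference between 0 and 56 scheduled post-treatment days comes directly from the two documents. The resulting dilution, a factor of (1 − f), applies whenever any child transitions and percentages are taken over the Safety N. Early withdrawals who miss the follow-up visit add to it in the same way.

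Its size cannot be fixed from the documents: every value of p and f above is assumed, and the divisor is inferred from the Population column. The primary on-treatment safety results are not in question. This is a change the SAP should make, confined to descriptive post-treatment displays.

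**What to change.** - Update the SAP to Amendment 5.
- For the five tables, use as denominator the Part B Safety children observed beyond last dose plus 28 days: those not transitioning, and withdrawn children followed past that point. Show this n and the number transitioning in each dose column.
- Label the result as incidence among children followed post-treatment, not in the whole cohort.
- In SAP Section 10.3.1, define the end of Part B for children with no Visit 23.
- For Part B tables not limited by phase, footnote the 52- and 60-week collection windows, or split by phase where this is not already done.

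The followed-up subset can be derived from visit and dose dates already collected. Neither document describes a field recording transition, so the sponsor should confirm that it is captured. The cost is SAP wording and modest programming, with a smaller N and less precise percentages. If very few children in a column are followed, counts with the adverse event listing will say more than a percentage.

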10.10.3.5. Safety Figures

Safety : Figures					
No.	Population	IDSL / TST ID / Example Shell	Title	Programming Notes	Deliverable [Priority]
Laboratory					
3.3.	Safety	LIVER9	Scatter Plot of Maximum vs. Baseline for ALT (Part B)		SAC
3.4.	Safety	LIVER9	Scatter Plot of Maximum ALT vs. Maximum Total Bilirubin (Part B)		SAC

10.10.3.6. ICH Listings

ICH : Listings					
No.	Population	IDSL / TST ID / Example Shell	Title	Programming Notes	Deliverable [Priority]
Subject Disposition					
52.	Safety	ES2	Listing of Reasons for Premature Study Withdrawal (Part B)		SAC
Concomitant Medication					
53.	Safety	CM6	Relationship Between ATC Level 1, Ingredient and Verbatim Text (Part B)	Include all asthma and non-asthma concomitant medications (including those given for exacerbation and rescue use)	SAC
Protocol Deviations					
54.	Safety	DV2	Listing of Important Protocol Deviations (Part B)		SAC
Blood Eosinophils					
55.	PDe		Listing of Blood Eosinophil Data (10 ⁹ /L) (Part B)	See format of Efficacy Listing 18 (200862 'final' reporting effort)	SAC
Exacerbations					
56.	PDo		Listing of Exacerbations (Part B)	See format of Efficacy Listing 17 (200862 'final' reporting effort) Include Pre, on-treatment and Post-treatment events within Part A (See Section 10.4.2)	SAC
Exposure					
57.	Safety	EX3	Listing of Study Treatment Data (Part B)		SAC
Adverse Events					
58.	Safety	AE8	Listing of All Adverse Events (Part B)		SAC

ICH : Listings					
No.	Population	IDSL / TST ID / Example Shell	Title	Programming Notes	Deliverable [Priority]
59.	Safety	AE7	Listings of Subject Numbers for Individual Adverse Events (Part B)		SAC
60.	Safety	AE2	Listing of Relationship Between Adverse Event System Organ Classes, Preferred Terms, and Verbatim Text (Part B)		SAC
61.	Safety	AE8	Listing of all Fatal Adverse Events (Part B)		SAC
62.	Safety	AE8	Listing of Non-Fatal Serious Adverse Events (Part B)		SAC
63.	Safety	AE14	Listing of Reasons for Considering as a Serious Adverse Event (Part B)		SAC
64.	Safety	AE8	Listing of Adverse Events Leading to Permanent Discontinuation of Study Treatment or Withdrawal from Study by Overall Frequency (Part B)		SAC
65.	Safety		Listing of Adverse Events Defined by the Investigator as a Systemic (non-allergic or allergic/hypersensitivity) Injection Reaction (Part B)	See format of Safety Listing 26 (200862 'final' reporting effort)	SAC
66.	Safety		Listing of Adverse Events Defined by the Investigator as a Local Injection Site Reaction (Part B)	See format of Safety Listing 27 (200862 'final' reporting effort)	SAC
67.	Safety		Listing of AEs meeting Anaphylaxis Criteria (Part B)	See format of Safety Listing 28 (200862 'final' reporting effort)	SAC
68.	Safety		Listing of Serious Cardiac, Vascular and Thromboembolic (CVT) AEs (Part B)	See format of Safety Listing 29 (200862 'final' reporting effort)	SAC
69.	Safety		Listing of Serious Ischemic AEs (Part B)	See format of Safety Listing 30 (200862 'final' reporting effort)	SAC
70.	Safety		Listing of Malignancies (Part B)	See format of Safety Listing 31 (200862 'final' reporting effort)	SAC

ICH : Listings					
No.	Population	IDSL / TST ID / Example Shell	Title	Programming Notes	Deliverable [Priority]
71.	Safety		Listing of Opportunistic Infections (Part B)	See format of Safety Listing 32 (200862 'final' reporting effort)	SAC
Cardiovascular Events					
72.	Safety		Listing of Investigator Reported Cardiovascular Events: Arrhythmias (Part B)	See format of Safety Listing 33 (200862 'final' reporting effort)	SAC
73.	Safety		Listing of Investigator Reported Cardiovascular Events: Congestive Heart Failure (Part B)	See format of Safety Listing 34 (200862 'final' reporting effort)	SAC
74.	Safety		Listing of Investigator Reported Cardiovascular Events: Cerebrovascular Events/Stroke (Part B)	See format of Safety Listing 35 (200862 'final' reporting effort)	SAC
75.	Safety		Listing of Investigator Reported Cardiovascular Events: Deep venous Thrombosis/ Pulmonary Embolism (Part B)	See format of Safety Listing 36 (200862 'final' reporting effort)	SAC
76.	Safety		Listing of Investigator Reported Cardiovascular Events: Myocardial Infarction/Unstable Angina (Part B)	See format of Safety Listing 37 (200862 'final' reporting effort)	SAC
77.	Safety		Listing of Investigator Reported Cardiovascular Events: Peripheral Arterial Thrombosis Embolism (Part B)	See format of Safety Listing 38 (200862 'final' reporting effort)	SAC
78.	Safety		Listing of Investigator Reported Cardiovascular Events: Pulmonary Hypertension (Part B)	See format of Safety Listing 39 (200862 'final' reporting effort)	SAC
79.	Safety		Listing of Investigator Reported Cardiovascular Events: Revascularisation (Part B)	See format of Safety Listing 40 (200862 'final' reporting effort)	SAC
80.	Safety		Listing of Investigator Reported Cardiovascular Events: Valvulopathy (Part B)	See format of Safety Listing 41 (200862 'final' reporting effort)	SAC
81.	Safety		Listing of Investigator Reported Cardiovascular Events: All Cause Deaths (Part B)	See format of Safety Listing 42 (200862 'final' reporting effort)	SAC

ICH : Listings					
No.	Population	IDSL / TST ID / Example Shell	Title	Programming Notes	Deliverable [Priority]
Immunogenicity					
82.	Safety		Listing of Immunogenicity Results (Part B)	See format of Safety Listing 43 (200862 'final' reporting effort)	SAC
Laboratory Data					
83.	Safety		Listing of Urinalysis (Part B)	See format of Safety Listing 44 (200862 'final' reporting effort)	SAC
Liver Event					
84.	Safety	LIVER5	Listing of Liver Monitoring/Stopping Event Reporting (Part B)		SAC
85.	Safety	LB5	Chemistry Results for Subjects Meeting Liver Monitoring/Stopping Event Criteria (Part B)	Subset for subjects in above Liver Monitoring/Stopping Event listing	SAC
86.	Safety	MH2	Listing of Medical Conditions for Subjects with Liver Stopping Events (Part B)		SAC
87.	Safety	SU2	Listing of Substance Use for Subjects with Liver Stopping Events (Part B)		SAC
88.	Safety	LIVER13	Listing of Subjects Meeting Hepatobiliary Laboratory Criteria Post-Baseline (Part B)		SAC
Electrocardiogram (ECG)					
89.	Safety	EG6	Listing of ECG Findings for Abnormal Interpretations (Part B)	See format of Safety Listing 7.32 (MEA115588 'final' reporting effort)	SAC

